#### **7.4.3 Health Search IMS Health Longitudinal Patient Database (HSD) – Italy**

The Italian arm of the study will use the Health Search IMS Health Longitudinal Patient Database (HSD), a longitudinal observational database that is representative of the Italian general population. It was established in 1998 by the Italian College of General Practitioners ([Filippi et al 2005](#)). The HSD contains data from computer-based patient records from a selected group of GPs (covering a total of 1.5 million patients) located throughout Italy. These GPs voluntarily agreed to collect data for the database and attend specified training courses. The database includes information on the age, gender, and identification of the patient, and GP registration information, which is linked to prescription information, clinical events and diagnoses, hospital admission, and causes of death. All diagnoses are coded according to the International Classification of Diseases, 9th Revision, Clinical Modification (ICD-9 CM). Drug names are coded according to the ATC classification system. To be included in the study, GPs must have provided data for at least one year and meet standard quality criteria pertaining to: levels of coding, prevalence of well-known diseases, and mortality rates ([Cricelli et al 2003](#)). The HSD complies with EU, guidelines on the use of medical data for research. HSD has been used as a database for a number of peer reviewed publications on the prevalence of disease conditions, drug safety, and prescription patterns in Italian primary care ([Cazzola et al 2011](#)). Approval for use of data is obtained from the Italian College of General Practitioners.

Dose must be inferred from the strength and according to the dosing regimens of the respective Summary of Product Characteristics (SmPC) for the other drugs. Around 50% of prescribed daily dosages are also imputed by GPs.

As this is a primary care database, information on specialist prescribing, drug dispensing, and actual drug intake is missing.

#### **7.4.4 Agenzia Regionale di Sanità della Toscana (ARS) – Italy**

The Italian National Healthcare System is organized at a regional level: the regions are responsible to provide to all their inhabitants a prespecified level of assistance, with a national tax-based funding. The Tuscany Region has around 3.6 million inhabitants. The ARS database comprises all the tables that are collected by the Tuscany Region to account for the healthcare delivered to the persons that are officially resident in the region. Moreover, ARS collects tables from regional initiatives. All tables in the ARS database can be linked at the individual level.

ARS is allowed by regional law to conduct studies using its database. To conduct a study in pharmacoepidemiology, ARS requires full compliance with the ENCePP Code of Conduct.

The ARS database routinely collects primary and secondary care prescriptions of drugs for outpatient use and is able to link them at the individual level with hospital admissions, admissions to emergency care, records of exemptions from copayment, diagnostic tests and procedures, and causes of death. The lack of availability of outpatient diagnoses or laboratory data in ARS is expected to possibly shift capture of events to the more severe forms of myotoxicity and hepatotoxicity (i.e., less serious events with only increases of laboratory parameters, or the ones only requiring an outpatient visit would be missed). Acute pancreatitis is expected to ultimately result in hospitalization and is therefore not expected to be affected.

The database was established in 1999. The ARS database is updated approximately every month, with a lag time of 3-4 months. Transactional data may still be incomplete, and each year's data is consolidated by the end of March every year.

ARS and HSD do not have the same catchment area, therefore, overlap is limited (< 2%). Whereas ARS is only capturing information from the region of Tuscany, HSD is collecting information from a selected sample of GPs across the entire country (including Tuscany). However, as sacubitril/valsartan initially is mostly prescribed by specialists (cardiologists, internists, geriatricians; due to reimbursement policy), which is captured in ARS but not captured in HSD, there is a small risk of overlap between ARS and HSD. However, as sacubitril/valsartan exposure prevalence identified in HSD is very low, the risk of overlap in this study is considered negligible.

#### **7.4.5 PHARMO Database Network – the Netherlands**

The PHARMO Database Network is a population-based network of electronic healthcare databases and combines data from different primary and secondary healthcare settings in the Netherlands. These different data sources, including data from general practices, in- and outpatient pharmacies, clinical laboratories, hospitals, cancer, pathology and perinatal registries,

are linked on a patient level through validated algorithms. Detailed information on the methodology and the validation of the used record linkage methods can be found elsewhere ([van Herk-Sukel et al 2010](#)).

The longitudinal nature of the PHARMO Database Network system enables to follow-up more than 4 million (25%) residents of a well-defined population in the Netherlands for an average of ten years. However, the data collection period, catchment area, and overlap between data sources differ. Therefore, the final cohort size will depend on the data sources included. As data sources are linked on an annual basis, the average lag time in data availability is one year. All electronic patient records in the PHARMO Database Network include information on age, sex, socioeconomic status, and mortality. Other available information depends on the data source used. To address the objectives of the present study the following PHARMO databases will be used: General Practitioner Database, Out-patient Pharmacy Database and Hospitalisation Database.

GP Database comprise data from electronic patient records registered by GPs. The records include information on diagnoses and symptoms, laboratory test results, referrals to specialists, and healthcare product/drug prescriptions. The prescription records include information on type of product, prescription date, strength, dosage regimen, quantity, and route of administration. Drug prescriptions are coded according to the ATC Classification System. Diagnoses and symptoms are coded according to the ICPC, which can be mapped to ICD codes, but can also be entered as free text.

The Out-patient Pharmacy Database comprises GP or specialist prescribed healthcare products dispensed by outpatient pharmacies. The dispensing records include information on type of product, date, strength, dosage regimen, quantity, route of administration, prescriber specialty, and costs. Drug dispensing are coded according to the ATC Classification System.

The Hospitalisation Database comprises hospital admissions for more than 24 hours and admissions for less than 24 hours for which a bed is required from the national Dutch Hospital Data Foundation. The records include information on hospital admission and discharge dates, discharge diagnoses and procedures. Diagnoses are coded according to the ICD codes and procedures are coded according to the Dutch Hospital Data Foundation registration system for procedures which links to the Dutch Healthcare Authority (NZA) declaration codes and the Dutch Classification of Procedures.

Combined GP, out-patient pharmacy and hospitalisation data currently cover a catchment area representing 1.2 million residents.

#### **7.4.6 Aarhus University Prescription Database – Denmark**

The Aarhus University Prescription Database comprises clinical and prescription data on the population of former North-Jutland, Aarhus, Rinkjebing and Viborg counties, which since 2007 are called the Central Denmark Region and the North Denmark Region. This population covers a total of 1.8 million inhabitants and is representative of the population of Denmark ([Ehrenstein et al 2010](#)). Data available on these subjects comprise their eligibility, dispensing data,

hospitalizations and procedures. Moreover, the population can also be linked to other National Danish registries. Dispensing data comprise the filled prescriptions for all ambulatory patients and contains information about the name of the drug, ATC code, package identifier (strength and route of administration), and the date of refill. These data can be linked to the national registry of patients that comprises information on admissions to Danish somatic hospitals, emergency rooms and outpatient clinics. Diagnosis codes and procedures are registered. These databases have been used in numerous studies and are proven valid for pharmacoepidemiological research ([Sørensen and Larsen 1994](#)).

Dose must be inferred from the strength, and according the dosing regimens of the respective SmPC of the other drugs. The main drawbacks of the Aarhus University Prescription Database are a lack of nationwide coverage and the absence of data of certain medication types (non-reimbursed drugs, OTC drugs or drugs dispensed directly to hospital patients or outpatient clinics).

#### **7.4.7 German Pharmacoepidemiological Research Database (GePaRD) – Germany**

Since 2004, the Leibniz Institute for Prevention Research and Epidemiology – BIPS has been working on the establishment and maintenance of GePaRD. GePaRD is based on claims data from statutory health insurance (SHI) providers, and currently includes information on about 25 million persons who have been insured with one of the participating providers since 2004. Per data year, there is information on approximately 20% of the general population from all geographical regions of Germany.

In addition to demographic data, GePaRD contains information on drug dispensing, outpatient and inpatient services, and diagnoses starting with the year 2004. New data are added on an annual basis. Before data are entered into the GePaRD database they are pseudonymized and validated through numerous plausibility checks. The entire process from data delivery to availability for studies can take up to two years, e.g., data from the year 2015 cannot be used before 2017.

GePaRD is linked via the central pharmaceutical number to information from a central pharmaceutical reference database established at Leibniz Institute for Prevention Research and Epidemiology – BIPS ([Leibniz Institute for Prevention Research and Epidemiology – BIPS 2017](#)). GePaRD is compliant with EU guidelines on the use of medical data for medical research and has been validated for pharmacoepidemiological research (e.g. [Pigeot and Ahrens 2008](#), [Ohlmeier et al 2016](#)).

### **7.5 Study size/power calculation**

[figure not shown]
Since the primary objective of the study is to estimate the IR of angioedema and other safety events of interest with sacubitril/valsartan, [Figure 7-3](#) presents CIs expected for angioedema, the rarest of all the events, given different sample sizes. An IR of angioedema following sacubitril/valsartan was set to be 5.5/1,000 PYs, based on an IR of 2.9/1,000 PYs following

ACEI estimated via meta-analysis, using data up to 1 year from three observational retrospective cohort studies (Figure 7-5 and Table 7-9, random effect Poisson model using data from Burkhart et al 1996, Miller et al 2008, and Toh et al 2012) and set to an IR ratio sacubitril/valsartan/ACEI of 1.9, based on the results of the double-blind part of the pivotal phase III study PARADIGM (McMurray et al 2014). Figure 7-4 shows expected CIs for the hazard ratio (HR) of sacubitril/valsartan versus ACEI for angioedema (exploratory objective [see Section 6.3]) for different sample sizes. In addition to previous assumptions on sacubitril/valsartan and ACEI IRs, the same exposure for sacubitril/valsartan and ACEIs was added.

[figure not shown]
With these assumptions, it is aimed to approximately have 24,000 PY of exposure with sacubitril/valsartan, which will provide an estimated IR of 5.5/1000 PY [95% CI: 4.6-6.5], if we observe 132 angioedema cases.

**Figure 7-3**      **Examples of confidence intervals for the incidence rate of angioedema after exposure to sacubitril/valsartan**

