### Study size

Based on estimates from forecasts, approximately 29,000 sacubitril/valsartan initiators may be included in this study with an accumulated 24,000 patient-years (PYs) of sacubitril/valsartan exposure. If 132 cases of angioedema are reported, this would allow estimating an incidence rate (IR) of 5.5/1,000 PYs with a 95% confidence interval (CI) ranging from 4.6 to 6.5. Feasibility assessments will provide information about how many potential patients initiating ACEIs will possibly be included in the study.

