In a meta-analysis including five randomized controlled trials with a total of 14,841 patients exposed to sacubitril/valsartan with follow-up ranging from 2 to 27 months, the collective percentage of angioedema was 0.5% in the sacubitril/valsartan arms versus 0.3% in the control arms (ACEIs/ARBs) (pooled odds ratio of 1.35; 95% confidence interval (CI): 0.45 to 4.1; p = 0.59) ([Dani et al 2021](#)). An additional recent systematic review and meta-analysis of randomized controlled trials (RCTs) did not find an increased angioedema risk of sacubitril/valsartan versus active control treatment overall (risk ratio: 1.72 [95% CI: 0.93-3.18] based on 15 RCTs), nor when compared to ACEIs (risk ratio: 0.87 [95% CI: 0.21-3.59] based on four RCTs) ([Martins et al 2021](#)).

The risk for angioedema associated with sacubitril/valsartan in every-day clinical practice is currently unknown and will be investigated in this non-interventional study. Based on the fourth interim analysis of study LCZ696B2014, the crude pooled IR of angioedema in association with use of sacubitril/valsartan (regardless of prior ACEI/ARB use) was of similar magnitude compared to ACEIs users treatment-naïve to ACEIs/ARBs) (i.e., 0.7 [95% CI: 0.4-1.1] per 1,000 PYs versus 1.0 [95% CI: 0.9-1.2] per 1,000 PYs) (██████████).

Angioedema is included in the Entresto® RMP as an identified risk.

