#### 7.7.1.2.2 Analyses of primary, secondary and exploratory objectives

For databases with a partial linkage to hospitalization data, the linked and unlinked subsets will be analyzed separately, to allow interpretation of additional hospital diagnoses in the analyses. This will be applied across all data analyses.

The COVID-19 pandemic has caused disruption of the health care systems from 2020 onward. In order to assess its impact on the analyses, the primary analysis will focus on the pre-COVID period, which is censored at 31 December 2019. The primary and secondary objectives (the period until the latest extraction date) will be assessed in the full study period as a sensitivity analysis.

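### The 24,000 PY target is still justified with an angioedema rate of 5.5 per 1,000 PY, about 8 times the study's own interim rate, so the expected case count and relative precision are out of date

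*Protocol*

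**What the plan says.** Section 7.5 builds the planning rate in two steps. It starts from an ACE inhibitor rate ("based on an IR of 2.9/1,000 PYs following" ACE inhibitors, from a meta-analysis of three cohort studies), then applies a ratio "set to an IR ratio sacubitril/valsartan/ACEI of 1.9", taken from the double-blind phase of the pivotal trial. The result is stated as "An IR of angioedema following sacubitril/valsartan was set to be 5.5/1,000 PYs". The target follows: "it is aimed to approximately have 24,000 PY of exposure with sacubitril/valsartan, which will provide an estimated IR of 5.5/1000 PY", with an interval of 4.6-6.5 if 132 cases occur. The abstract says the same: "If 132 cases of angioedema are reported, this would allow estimating an incidence rate (IR) of 5.5/1,000 PYs". Figure 7-4 uses these rates for the hazard ratio and assumes equal exposure in the two groups.

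Section 5.1 gives the study's own fourth-interim rates, for all sacubitril/valsartan initiators (cohort 1) and for treatment-naive ACE inhibitor users (cohort 4): "0.7 [95% CI: 0.4-1.1] per 1,000 PYs versus 1.0 [95% CI: 0.9-1.2] per 1,000 PYs". Section 7.5 does not mention them.

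Section 7.7.1.2.2 adds that "the primary analysis will focus on the pre-COVID period, which is censored at 31 December 2019".

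**The concern.** Two rates for the same event in the same cohort stand in one protocol version, and only the older one supports the study size. The 24,000 PY figure is still in use: Section 7.1.1 treats it as the required size, Table 4-1 makes it a trigger for ending data collection, and the amendment rationale calls the two added databases crucial for reaching it. The amendment relied on the fourth interim elsewhere, when it dropped the historical ACE inhibitor cohort (Sections 7.1.1 and 7.1.2), but left the sizing alone.

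A reader who takes Section 7.5 at face value expects more than a hundred angioedema cases. The number of cases governs the relative precision of the primary rate and the precision of the hazard ratios. It also limits what the per-database and week-by-week estimates can show.

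**Working it through.** **Reproducing the plan's figures**
- Ratio: (19/4,203) / (10/4,229) = 1.91, consistent with 1.9 (counts from Section 5.1).
- ACE inhibitor rate: a DerSimonian-Laird pool of the log rates in Table 7-9 gives 2.87 per 1,000 PY, consistent with 2.9.
- Planning rate: 2.9 × 1.9 = 5.51, used as 5.5.
- Cases: 5.5/1,000 × 24,000 = 132.
- Exact Poisson 95% limits for d cases in T person-years are χ²(0.025; 2d)/(2T) and χ²(0.975; 2d+2)/(2T). For 132 in 24,000 PY: 4.60-6.52 per 1,000 PY, as printed.

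**Size of the discrepancy**
- 5.5/0.7 = 7.9 against the interim estimate.
- 5.5/1.1 = 5.0 against its upper limit; 5.5/0.4 = 13.8 against its lower limit.

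**The same calculation at interim-based rates, 24,000 PY**

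| Rate per 1,000 PY | Expected cases | Cases used | Rate (exact 95% CI) | Relative limits | Width per 1,000 PY |
|---|---|---|---|---|---|
| 5.5 (plan) | 132.0 | 132 | 5.50 (4.60-6.52) | -16% / +19% | 1.92 |
| 1.1 | 26.4 | 26 | 1.08 (0.71-1.59) | -35% / +47% | 0.88 |
| 0.7 | 16.8 | 17 | 0.71 (0.41-1.13) | -42% / +60% | 0.72 |
| 0.4 | 9.6 | 10 | 0.42 (0.20-0.77) | -52% / +84% | 0.57 |

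Even at 1.1 per 1,000 PY, the Poisson probability of 132 or more cases is effectively zero. To show the scale, 132 cases at 0.7 would need 132/0.0007 ≈ 189,000 PY (120,000 at 1.1; 330,000 at 0.4).

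**Hazard ratio, equal exposure of 24,000 PY per group**

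Half-width factor = exp(1.96 × √(1/a + 1/b)), where a and b are the cases in each group.
- Plan: a = 132, b = 2.9 × 24 = 69.6. √(0.00758 + 0.01437) = 0.148, factor 1.34.
- Interim rates: a = 0.7 × 24 = 16.8, b = 1.0 × 24 = 24. √(0.0595 + 0.0417) = 0.318, factor 1.87.

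These factors ignore the loss of information from propensity score weighting and from pooling across databases.

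**Which person-years count**

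The 24,000 PY is a total-exposure target, but the primary analysis stops at 31 December 2019. Table 7-1 shows data beyond that date in every database except GePaRD. The protocol does not give the person-years lost, so the loss cannot be computed.

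**The case against.** The strongest defence is that nothing in Section 7.5 is miscalculated and nothing is promised outright. Both statements of the interval are conditional on 132 cases, and the figure titles call the intervals examples. That stands: this is an outdated assumption, not an arithmetic error.

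The second defence is about scale. The primary objective is an absolute rate with its interval, and on that scale the interim-based interval is narrower than the printed one (0.72 against 1.92 per 1,000 PY). That stands too. A reader might infer that 24,000 PY is too little for the primary objective, but the documents do not support this, because they never say whether absolute or relative precision is the aim.

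Third, the interim rate is crude and pooled. Section 7.7.1.1 leaves validated rates to the final analysis, and Section 7.7.1.2.3 will estimate cases missed by the narrow definition. This is a reason to show a range. It does not rescue 5.5, which is five times the upper interim limit.

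Three further inferences are tempting and fail:
- *The interim rates refute the ratio of 1.9.* The interim contrast sets all initiators, mostly pre-treated, against naive ACE inhibitor users. Section 7.1.1 says this contrast probably favours sacubitril/valsartan. The 1.9 comes from a randomised comparison.
- *Cohort 2 will have only one or two cases.* That uses a single 7.8% naive share (100 minus the 92.2% treated in a registry of prevalent disease, Section 7.1.1): 24,000 × 0.078 = 1,872 PY, or 1.3-1.9 cases at 0.7-1.0 per 1,000 PY. The 43% prior exposure in incident disease, cited in the same section, would give a 57% share: 13,680 PY and 9.6-13.7 cases. Neither figure measures naivety by the study's 365-day rule.
- *The 2019 cut-off removes much of the exposure.* GePaRD data end then in any case, and GePaRD supplied 4,724 of 5,185 initiators (91%) in the feasibility count. The loss may be modest.

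Finally, all comparisons are exploratory, and Section 7.9 already concedes that the naive comparison may be underpowered. This lowers the stakes for the hazard ratio but does not make the planning inputs current.

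**Conclusion.** The point holds as an unreconciled planning assumption. Section 7.5 and the abstract justify the target with a rate about 8 times the interim rate printed in the same document. At 24,000 PY about 17 cases are to be expected (10 to 26 across the interim interval), not 132, with a 95% CI near 0.41-1.13 per 1,000 PY. Relative precision is clearly worse and absolute precision is better. The hazard ratio interval is wider, with a half-width factor of about 1.87 instead of 1.34 under equal exposure.

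These figures assume simple Poisson counts, 24,000 PY actually contributing to the analysis, and a final rate close to the crude interim one. Validation could move that rate in either direction. The finding does not show that the study is too small for its primary objective, or that any planned analysis is wrong.

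**What to change.** - In Section 7.5, the abstract and Figures 7-3 and 7-4, restate expected cases and intervals at 0.4, 0.7 and 1.1 per 1,000 PY. Keep 5.5 as the original assumption, labelled as such, and note that the interim rate is crude and not validated.
- State whether absolute or relative precision is the target, and why 24,000 PY meets it.
- Base the figures on the person-years that count in the primary analysis (to 31 December 2019), and base the hazard ratio figure on the observed, unequal ACE inhibitor exposure. The sponsor holds both; the protocol gives ACE inhibitor patient counts (116,041 naive initiators in Section 7.1.1) but not their person-years.
- If a line for cohort 2 is added, use the naive share seen at the interim, or a range.

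The work is protocol text and two figures. Data collection is unaffected. The only cost is that the stated relative precision looks less favourable.

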**Assumed angioedema incidence 5.5 / 1000 PY**

**Figure 7-4** Examples of confidence intervals for the hazard ratio (HR) of angioedema after exposure to sacubitril/valsartan versus ACEI

**Table 7-9** Literature information for the meta-analysis of angioedema incidence rate following ACEIs

Reference	Database	Years	HF (%)	Number of Angioedema cases up to 1 year	Patients	Exposure Up to 1 year (PYs)	IR (per 1000 PYs)	95% LCL	95% UCL
Toh et al (2012)	Mini-sentinel	2001-2010	2.2	3301	1,845,138	753,105	4.38	4.24	4.54
Miller et al (2008)	VA	1999-2000	20.3	319*	195,192	143,623	2.22*	1.98*	2.48*
Burkhart et al (1996)	Medicaid	1986-1992	NA	168*	155,258	69,966	2.40*	2.05*	2.79*

[figure not shown]
ACEI = angiotensin converting enzyme inhibitor; IR = incidence rate; LCL = lower confidence limit; PY = patient-year; UCL = upper confidence limit; VA = Veterans Affairs; NA= not available; .HF= patients with HF diagnosis

\*Calculated from the published data

